studies by Hardaway et al evaluating fibrinolytic therapy for treatment of ARDS used urokinase and streptokinase, the more contemporary approach to thrombolytic therapy involves the use of tissue-type plasminogen activator (tPA) due to higher efficacy of clot lysis with comparable bleeding risk to the other fibrinolytic agents.

Hypothesis:

We hypothesize that administration of tPA to patients with COVID-19 associated severe ARDS will improve pulmonary gas exchange and oxygenation via a decrease in pulmonary vascular microthrombi.

Study Design:

This is a Phase IIa clinical trial, open label, with a modified stepped-wedge design, testing systemic administration of fibrinolytic therapy with alteplase (tPA) versus standard of care for patients infected with COVID-19 resulting in severe respiratory failure. The design is a rapidly adaptive, pragmatic clinical trial, with 3 interim analyses and 1 final look at the data. Pre-planned adaptations described below will be contemplated at each interim analysis or earlier if recommended by the Data Safety Monitoring Board (DSMB).

Inclusion Criteria: We will include adult patients ages 18-75 years old with known or suspected COVID-19 infection with a PaO₂/FiO₂ ratio < 150 or inferred PaO₂/FiO₂ ratio from SpO₂ if ABG is unavailable (Table) persisting for > 4 hours despite optimal mechanical ventilation management according to each institution's ventilation protocols, and a neurological exam without focal signs or new deficits at time of enrollment (if patient is on paralytics, patient has been aroused sufficiently to allow a neurological examination to exclude new focal deficits or has MRI/CT scan in the last 4.5 hours with no evidence of stroke. Finally, patients must be on the ventilator for ≤10 days to be eligible. Based on experience with critically ill patients, longer ventilation time may be associated with increased risk of bleeding. Patients will be enrolled based on clinical features, without consideration of language (using hospital interpreters and translated consent), race/ethnicity, or gender. A neurological exam or CT/MRI scan to demonstrate no evidence of an acute stroke is needed due to a recent case-report of large-vessel stroke as a presenting feature of COVID-19 in young individuals.⁴⁴

SPO2	FIO2														
	0.3	0.35	0.4	0.45	0.5	0.55	0.6	0.65	0.7	0.75	0.8	0.85	0.9	0.95	1
80%	148	127	111	98	89	81	74	68	63	59	55	52	49	47	44
81%	151	129	113	101	91	82	76	70	65	60	57	53	50	48	45

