- INR > 1.7 (with or without concurrent use of warfarin)
- Platelet count < 100 x 10⁹/L or history of HITT
- Fibrinogen < 300mg/dL
- Known abdominal or thoracic aneurysm
- History of CNS malignancy or CNS metastasis within past 5 years
- History of non-CNS malignancy within the past 5 years that commonly metastasizes to the brain (lung, breast, melanoma)
- Prisoner status

Patients will be sequentially assigned to one the following three groups as follows:

1. Group tPA50 will receive 50 mg of tPA intravenous bolus administration over 2 hours, given as a 10 mg push followed by the remaining 40 mgs over a total time of 2 hrs (not to exceed 0.9mg/kg dose). Immediately following the tPA infusion, 5000 U of UFH will be delivered and the heparin drip will be continued to maintain the activated partial thromboplastin time at 60-80sec (2.0 to 2.5 times the upper limit of normal). This tPA protocol is a modification of the GUSTO I to III trials.^{45,46}

2. Group tPA50 plus drip will receive 50 mg of tPA intravenous bolus administration over 2 hours, given as a 10 mg push followed by the remaining 40 mgs over a total time of 2 hrs (not to exceed 0.9mg/kg dose). Immediately following this initial tPA infusion, we will initiate a drip of 2 mg/hr tPA over the ensuing 24 hours (total 48 mg infusion) accompanied by an infusion of 500U/hour heparin during the tPA drip. After this, heparin dose will be increased slowly to maintain a PTT between 60 and 80 sec, titrated per attending's discretion.⁴⁷

3. Control: standard of care according to the institution's protocol for ARDS

Amendment Nov 4, 2020: please see below description for more detailed information on adaptation. The rationale for adjusting the tPA administration to a 50 mg bolus followed by a 2mg/hr infusion over the ensuing 24 hr is based on the facts that:

- 1) a convincing improvement in P/F was observed at 24 hr, but was lost over the ensuing 24 hr,
- 2) there was no discernable response to the second tPA bolus at the 24 hr time point,
- 3) we believe the initial 50 mg bolus has provoked fibrinolysis shutdown ;ie, PAI-1 generation in response to the tPA bolus blunting a response to a second bolus at 24 hr,
- 4) an infusion of low dose tPA will consume the PAI-1 generated in response to the initial tPA bolus and provide an additional fibrinolytic intervention over the ensuing 24 hr,

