All randomizations are conducted intra-hospital (i.e., no cluster randomization), to avoid the confounding effect of practice variation. Randomization will be conducted in blocks of 10 to allow better distribution between groups at each interim analysis. It will be done by the Data Coordinating Center (DCC) and automated in an web-based REDCap data collection instrument. Upon confirmed eligibility and consent, the REDCap will reveal the group assignment to institution's pharmacy, which will then release the drug if the patient is assigned to the intervention group (Group tPA50, Group tPA50+drip). Time zero is assigned as the time of randomization. We anticipate that each of the five centers will enroll 8-12 patients.

The figure below illustrates the initial planned sequential, stepped-wedge design and the proposed new design after the adaptations driven by the first interim analysis. Study will continue during the interim analyses, unless a safety issue occurs.

INITIAL DESIGN

NEW DESIGN AFTER 1st INTERIM ANALYSIS

Re-bolusing of tPA, at the same dose, is permitted in the tPA50 intervention group in those patients who show an initial transient response (>20% improvement of PaO₂/FiO₂ over pre-infusion of alteplase at any of the measurements at 2, 6, 12 or 18 hours, but <50% improvement of PaO₂/FiO₂ at 24 hours after randomization); the repeat dose will be given between 24 and 36 hours after the initial tPA administration.

The same EXCLUSION criteria apply to the second tPA (alteplase) bolus. The heparin drip should be stopped two hours before the second tPA (alteplase) and re-started after the second alteplase infusion ends, at the same dose as before the second alteplase.

Other modifications of the dosing are as follows:

- Fibrinogen monitoring:** For all tPA administration groups, fibrinogen levels will be measured before and after tPA IV bolus, 6 hours after the start of the infusion, then every 6 hours for first 24 hours, and once a day for 6 days following treatment intervention in all the groups (see detailed lab testing schedule below). **If fibrinogen levels fall below 300 mg/dL, the second bolus of tPA (alteplase) is NOT indicated.**

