- Heparin dosing for the tPA50 group and for after the 48mg tPA drip in the tPA50 drip group:** An infusion of unfractionated heparin infusion will be continued for up to 7 days or until the patient is extubated and has an O₂ requirement of ≤ 4L/min by nasal cannula, and titrated to maintain the activated partial thromboplastin time to 60-80sec (2.0 to 2.5 times the upper limit of normal) per attending's discretion. In case an additional tPA (alteplase) infusion is needed, the heparin drip should be stopped two hours before and re-started after the alteplase infusion ends, at the same dose as before the alteplase. The goal of this treatment is to prevent recurrent microvascular thrombotic hypoxemia or macrovascular complications (stroke, myocardial infarction or venous thromboembolism) due to possible rebound tPA effects causing hypercoagulability. Intravenous heparin is currently a standard of care (SOC) for COVID-19 patients in the ICU due to their extreme hypercoagulability.

Laboratory Measurements:

1. Arterial blood gases, fibrinogen and D-Dimer levels, PT/INR, aPTT, and CBC. Interval for measurement: before and after tPA IV bolus, 6 hours after the start of the infusion, then every 6 hours for first 24 hours, and once a day for 6 days following treatment intervention in all the groups.
2. Thrombelastography or ROTEM (where available) Interval for measurement: Before and after tPA bolus, 6 hours after the start of the infusion, and every 6 hours for the first 24 hours, then daily thereafter for 6 days or until discharge
3. Troponin and CRP pre-treatment and at 24 hours post-infusion
4. Total Bilirubin test pre-treatment (for baseline liver function)

Laboratory tests will follow the schedule below:

	ABG	CBC with platelet count	PT/INR	PTT	Fibrinogen	D-dimer	TEG or ROTEM	Troponin	CRP	Total Bilirubin
Pre-Treatment	X	X	X	X	X	X	X	X	X	X
After Treatment	X	X	X	X	X	X	X			
Hour 6	X	X	X	X	X	X	X			
Hour 12	X	X	X	X	X	X	X			
Hour 18	X	X	X	X	X	X	X			
Hour 24	X	X	X	X	X	X	X	X	X	
Hour 48	X	X	X	X	X	X	X			
Hour 72	X	X	X	X	X	X	X			
Hour 96	X	X	X	X	X	X	X			
Hour 120	X	X	X	X	X	X	X			
Hour 144	X	X	X	X	X	X	X			
Hour 168	X	X	X	X	X	X	X			

All patients enrolled in the trial, regardless of randomization group, will follow the above lab testing schedule. Total amount of blood to be collected during 7 days of study is 200mL. We are also planning on using the blood and other tissues leftover after the safety labs (discarded samples) for research purposes.

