- NIAID ordinal scale: The ordinal scale is an assessment of the clinical status as follows: 1) Death; 2) Hospitalized, on invasive mechanical ventilation or extracorporeal membrane oxygenation (ECMO); 3) Hospitalized, on non-invasive ventilation or high flow oxygen devices; 4) Hospitalized, requiring supplemental oxygen; 5) Hospitalized, not requiring supplemental oxygen - requiring ongoing medical care (COVID-19 related or otherwise); 6) Hospitalized, not requiring supplemental oxygen - no longer requires ongoing medical care; 7) Not hospitalized, limitation on activities and/or requiring home oxygen; 8) Not hospitalized, no limitations on activities. (combined items 7 and 8 as our study is limited to hospital)

- 48 hour in-hospital mortality
- 14 days in-hospital mortality
- 28 days in-hospital mortality
- ICU-free days (up to 28 days)
- In-hospital coagulation-related event-free (arterial and venous) days (up to 28 days)
- Ventilator-free days (up to 28 days)
- Successful extubation (no re-intubation for >3 days after initial extubation)
- Successful weaning from paralysis for > 3 days after initial termination
- Survival to discharge

Sample size and Power Analysis: (Pass, 14.0, NCSS, LLC, Kaysville, Utah, USA)

We anticipate that each of the five centers will enroll 8-12 patients. Sample size and power Analysis was conducted using Pass, vs 14.0 (NCSS, LLC, Kaysville, Utah, USA) and focused on the primary outcome as defined above. Sample size assumptions:

- power=80%, confidence=95%, and 4 sequential tests(3 interim+1 final), using the Pocock spending function to determine test boundaries,
- potential improvement assumptions based on a previous study ⁴⁰ with appropriate(e.g., Denver) altitude correction as well as mean baseline PaO₂/FiO₂=149 with an overestimated standard deviation of 100,
- design effect=1.12 due to the study's multicenter nature (intra-class correlation coefficient=0.03, average cluster=5);
- ~20% inflation to account for premature death

A sample size of 50 (25 in each intervention group and 25 in the control group) patients detects a >70% improvement in PaO₂/FiO₂ between intervention groups (both tPA50 and tPA 50 plus drip) and controls, and >91% improvement in PaO₂/FiO₂ between intervention tPA 50 plus drip) and controls. Recruitment will assume at least 30% increase to account for refusal or inability to consent.

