Worsening of neurological function	Clinical neurological exam and imaging if	Clinical exam pre, during and immediately post alteplase infusion; every 6 hours post alteplase infusion up to 24 hours;	GCS decrease of >=2 points or focal deficit within 24 hours of study drug infusion or new

Serious Events	Adverse	Method for safety check	Safety check frequency	Cessation rule *
		applicable per care provider's decision. Most patients will use GCS without verbal component	at least every 24 hours after alteplase infusion during heparin infusion or more frequently if any abnormality detected. Imaging per attending's discretion.	hemorrhage on CT-Scan or MRI
Worsening pulmonary function	of	Arterial blood gas and ventilation indices		≥30% PaO ₂ /FiO ₂ baseline reduction
External bleeding		Clinical exam	Clinical exam pre, during and immediately post alteplase infusion; every 6 hours post alteplase infusion up to 24 hours; at least every 24 hours after alteplase infusion during heparin infusion or more frequently if any abnormality detected.	Unresponsive to compression
Gastro-intestinal bleeding	(GI)	Clinical exam and hemoglobin	Clinical exam pre, during and immediately post alteplase infusion; every 6 hours post alteplase infusion up to 24 hours; at least every 24 hours after alteplase infusion during heparin infusion or more frequently if any abnormality detected. Endoscopic exam per attending's discretion.	Hemoglobin reduction >3g/dL within 24 hours of study drug intervention or requiring RBC transfusion with suspected GI bleeding
Hemoptysis		Clinical exam	Clinical exam pre, during and immediately post alteplase infusion; every 6 hours post alteplase infusion up to 24 hours; at least every 24 hours after alteplase infusion during heparin infusion or more frequently if any abnormality detected.	Persistent hemoptysis for ≥4 hours or compromising airway

Adverse Events	Method for safety check	Safety check frequency	Cessation rule *
		Endoscopic exam per attending's discretion.	
Hematuria	Clinical exam	Clinical exam pre, during and immediately post alteplase infusion; every 6 hours post alteplase infusion up to 24 hours; at least every 24 hours after alteplase infusion during heparin infusion or more frequently if any abnormality detected. Endoscopic exam per attending's discretion.	Persistent hematuria for ≥ 4 hours or urinary obstruction

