### 6.5. Pre-planned subgroup analyses

We anticipate the following subgroup analyses, which will assist in determining whether there is a subgroup of patients for whom the intervention is more beneficial/harmful.

- Baseline PaO2/FiO2 <100 and <50
- Hemodynamic instability with vasopressors
- Age <35, <50, <65 years
- D-Dimers median levels
- Fibrinolysis shutdown (by TEG or ROTEM)
- Fibrinogen median levels
- Prone/supine positioning
- Requirement of re-bolusing of alteplase
- Received dose of alteplase as premature death or adverse event or other reasons may preclude the administration of complete treatment
- Elimination of centers contributing <2 cases.

Additional subgroup analyses may be defined at an interim analysis and will be added for the subsequent interim analyses. This will be documented by filing another version of this SAP with the IRBs, DSMB, funder and FDA.

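### The re-bolus rule does not repeat the entry neurological condition for patients on paralytics before a second alteplase dose

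*Protocol*

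**What the plan says.** **Entry.** The Protocol (Inclusion Criteria) and SAP 5.2 require a neurological exam free of new deficits at enrollment. For a patient on paralytics, the test is this: "patient has been aroused sufficiently to allow a neurological examination to exclude new focal deficits or has MRI/CT scan in the last 4.5 hours". Any such scan must be free of stroke. The protocol's reason is a report of stroke as a first sign of COVID-19. The condition appears in neither document's exclusion list.

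**Second bolus.** Under the Protocol's Design section, a tPA50 patient may be re-bolused at the same dose. The PaO2/FiO2 must have risen by more than 20% at 2, 6, 12 or 18 hours but be less than 50% above baseline at 24 hours. On timing, "the repeat dose will be given between 24 and 36 hours after the initial tPA administration". On eligibility, "The same EXCLUSION criteria apply to the second tPA (alteplase) bolus". Heparin is paused two hours beforehand, and fibrinogen under 300 mg/dL rules the bolus out. The SAP has no re-bolus rule of its own.

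**Safety monitoring.** The Protocol's safety-check table and SAP section 7 call for clinical exams around alteplase infusion and six-hourly over the following day. For neurological function, "Most patients will use GCS without verbal component", and imaging is at the attending's discretion. Drug stops for a GCS fall of 2 or more points, a focal deficit, or new hemorrhage on a scan.

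**The concern.** The sponsor judged that an ordinary exam is not enough in a paralysed patient and made arousal or recent imaging mandatory before the first dose. The second dose is the same drug at the same dose, yet the rule carries over only the exclusion list. The stroke and seizure exclusions do carry over, but they bar only an event that someone has recognised.

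The situation is foreseeable. Paralysis is expected in this population, because one secondary outcome is "Successful weaning from paralysis for > 3 days after initial termination". Stroke remains on the protocol's list of worries after the first dose: the heparin regimen is meant to prevent "macrovascular complications (stroke, myocardial infarction or venous thromboembolism) due to possible rebound tPA effects causing hypercoagulability". What is at stake is alteplase given to a patient with an unrecognised stroke or intracranial hemorrhage.

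The benefit on the other side looks modest. The November 2020 rationale reports that "there was no discernable response to the second tPA bolus at the 24 hr time point", though from few patients.

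**Working it through.** The plan states no figure for this point, so the check compares texts and adds some simple arithmetic.

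**1. What carries over**

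| Condition | Before first bolus | Before second bolus |
|---|---|---|
| Exclusion criteria, including known stroke | Required | Required |
| Fibrinogen at least 300 mg/dL | Required | Required |
| Clinical exam (safety table) | Required | Required, if the table covers every alteplase infusion |
| If on paralytics: arousal exam, or CT/MRI within 4.5 h | Required | Not stated |

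Only the last row is missing.

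**2. Patient paralysed and unexaminable continuously since entry**

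Assume the standard GCS, which the documents do not set out. Without the verbal part, the floor is eye 1 + motor 1 = 2. A patient already at 2 cannot fall by 2 points, so that stop rule cannot trigger. Limb or facial weakness cannot be seen either. Pupils can still be examined, but the table names no pupil check and normal pupils do not exclude a stroke. Discretionary imaging apart, no required later check could readily show one.

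**3. Patient aroused at entry and re-paralysed, or paralysed only later**

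This patient has had informative exams. If paralysis were scored literally, the score would drop to 2. That is a fall of 2 or more unless the earlier score was 2 or 3, so the stop rule would be met. A clinician might instead record the score as untestable. The documents do not say which, and they define no GCS baseline. Either way, the re-bolus rule asks for no current arousal exam or scan.

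**4. Age of an entry scan at the second bolus (patients who entered by CT/MRI only)**

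- Least: 24 h after the first alteplase; 24 / 4.5 = 5.3 times the limit.
- Most: 36 + 4.5 = 40.5 h, plus any delay from enrollment to infusion; 40.5 / 4.5 = 9.0 times the limit.

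An entry scan therefore cannot meet the same condition again.

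**5. Heparin exposure between boluses**

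Count from the start of the first 2-hour infusion, with heparin stopped 2 hours before the second bolus: 24 − 2 − 2 = 20 h to 36 − 2 − 2 = 32 h. These are upper figures for time at the target aPTT, because titration is left to the attending.

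**6. Reach**

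This version follows the first interim analysis at 10 patients. At 1:1 allocation (an assumption):

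- tPA50 used for patients 11 to 20: (20 − 10) / 2 = 5 patients.
- tPA50 kept to n = 50 under the 50% improvement branch: (50 − 10) / 2 = 20 patients.

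The smaller figure looks likelier. The amendment rationale says that the 24-hour gain was lost over the next 24 hours, and SAP 3.1 describes patients after the 20th going to the drip arm. Only paralysed transient responders count, and their share is not given.

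**The case against.** The strongest reply is that the protocol already leaves room to act safely. Re-bolusing is permitted, not required. The attending can stop drug or order imaging at any time. The stroke exclusion carries over, and the inclusion text says that an exam or scan is needed to show no acute stroke, so a site could reasonably use that method when it re-applies the exclusion. Few patients are involved, and some may already have been treated, because enrollment continues during interim review. All of this stands and keeps the point small. It does not supply the missing rule: at entry the same matter was not left to discretion.

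A reader might infer more than the text supports, in five ways:

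- *That no neurological check precedes the second bolus.* The safety table's pre-infusion exam can be read as covering every alteplase infusion.
- *That the GCS stop rule can never trigger in a paralysed patient, or that the last informative check always predates the first dose.* Both hold only for patients unexaminable continuously since entry.
- *That the check is always 5 to 9 times out of date.* That multiple applies only to patients who entered by CT/MRI. The entry arousal exam carries no 4.5-hour limit, and the split between the two routes is not given.
- *That the protocol treats heparin as raising the stroke risk.* The sentence that names stroke presents heparin as the protection.
- *That a patient with a cessation event could still be re-bolused.* On its natural reading, the cessation table already bars further drug.

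**Conclusion.** The gap is real and narrow. Followed as written, the re-bolus rule lets a transient responder who is paralysed at 24 to 36 hours receive a second bolus without the arousal exam or recent scan required before the first. The weakness is clearest for a patient unexaminable since entry. Patients aroused and re-paralysed, or paralysed later, are in a better position but can also be re-bolused without a current check.

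Severity is minor: at most about 5 further tPA50 patients, or about 20 on the less likely branch, and only a subset of those. No event count can be given. Power, sample size and alpha are unaffected.

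Confidence in the missing text is high. The size rests on 1:1 allocation. The GCS argument rests on the standard scale and on continuous paralysis since entry.

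**What to change.** Add one sentence to the re-bolus rule in the Protocol's Design section. Before the second bolus, the neurological condition from the inclusion criteria must be met again: an exam without new deficit or, in a patient on paralytics, arousal for that exam or a stroke-free CT/MRI within the last 4.5 hours. Otherwise the bolus is withheld and the reason is entered in REDCap. Because withholding is the default, no arousal or transport for imaging is forced.

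The cost is a short protocol amendment with its approvals, one REDCap field, and some paralysed patients who go without a second bolus. Received dose then becomes linked to paralysis status. That must be kept in mind when reading the dose comparison in SAP 6.4 and, in SAP 6.5, the re-bolusing subgroup and the one defined as "Received dose of alteplase as premature death or adverse event or other reasons may preclude the administration of complete treatment". The intent-to-treat comparison still groups patients as randomized.

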### Section 3: Study Methods

**3.1. Trial design** Multicenter, pragmatic, randomized, open label, rapidly adaptive, controlled, clinical trial

The trial has a novel design with modified stepped-wedge and adaptive features in order to rapidly identify the intervention group with the highest chance of benefit. This unconventional design is appropriate for the current circumstances of the pandemic caused by a new, lethal and morbid virus infection (COVID-19) for which no known treatment exists. The below figure illustrates the design. In brief, the patients will be sequentially assigned to one of three following groups:

[figure not shown]
[figure not shown]
- Group tPA50 will receive 50 mg of tPA intravenous bolus administration over 2 hours, given as a 10 mg push followed by the remaining 40 mgs over a total time of 2 hrs (not to exceed 0.9mg/kg dose). Immediately following the tPA infusion, 5000 U of UFH will be delivered and the heparin drip will be continued to maintain the activated partial thromboplastin time at 60-80sec (2.0 to 2.5 times the upper limit of normal). This tPA protocol is a modification of the GUSTO I to III trials. 44,45
- Group tPA50 plus drip will receive 50 mg of tPA intravenous bolus administration over 2 hours, given as a 10 mg push followed by the remaining 40 mgs over a total time of 2 hrs (not to exceed 0.9mg/kg dose). Immediately following this initial tPA infusion, we will initiate a drip of 2 mg/hr tPA over the ensuing 24 hours (total 48 mg infusion) accompanied by an infusion of 500 U/hr heparin during the tPA drip. After this, heparin dose will be increased slowly to maintain a PTT between 60 and 80 sec, titrated per attending's discretion.
- Control: institution's protocol for ARDS

In order to rapidly accrue patients in one intervention group with a concurrent control, the first 10 patients will be randomly assigned to Group tPA50 or Control (Standard-of-care) when the first interim analysis occurs. If no stopping criteria are met, the next 10 patients are randomly

assigned to Group tPA50 or Control when the second interim analysis is done. If no criteria for stopping or dropping an arm are met, the next 10 patients are randomly assigned to Group tPA50 plus drip or Control when the third interim analysis is done. Finally, if no criteria for stopping or dropping an arm are met, the trial progresses with patients being randomized to Group tPA50 plus drip or Control up to the final analysis at n=50.

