### 3.2. Sample size

We anticipate that each of the five centers will enroll 8-12 patients. Sample size and power Analysis was conducted using Pass, vs 14.0 (NCSS, LLC, Kaysville, Utah, USA) and focused on the primary outcome as defined above.

Sample size assumptions:

- power=80%, confidence=95%, and 4 sequential tests(3 interim+1 final), using the Pocock spending function to determine test boundaries,
- potential improvement assumptions based on a previous study 40 with appropriate(e.g., Denver) altitude correction as well as mean baseline PaO2/FiO2=149 with an overestimated standard deviation of 100,
- design effect=1.12 due to the study's multicenter nature (intra-class correlation coefficient=0.03, average cluster=5);
- ~20% inflation to account for premature death

---

 Urbaniak, G. C., & Plous, S. (2013). Research Randomizer (Version 4.0) [Computer software]. Retrieved on April 10, 2020, at <http://www.randomizer.org/>

A sample size of 50 (25 in each intervention group and 25 in the control group) patients detects a >70% improvement in PaO2/FiO2 between intervention groups (both tPA50 and tPA 50 plus drip) and controls, and >91% improvement in PaO2/FiO2 between intervention tPA 50 plus drip) and controls. Recruitment will assume at least 30% increase to account for refusal or inability to consent.

**Consent: We anticipate consenting enough patients to result in 50 eligible patients, thus we plan on a max of 60, to be re-evaluated during each of the interim analyses. LAR, as defined by the state and institutions legislation/policies, will be able to consent.**

The table below shows the details of the interim analyses with the Pocock spending method:

Look	N of Patients	Lower Bndry	Upper Bndry	Nominal Alpha	Inc Alpha	Total Alpha	Inc Power	Total Power
1	10	-2.43798	2.43798	0.015	0.015	0.015	0.18976	0.190
2	20	-2.42677	2.42677	0.015	0.011	0.026	0.25179	0.442
3	30	-2.41014	2.41014	0.016	0.009	0.035	0.21191	0.653
4	50	-2.39658	2.39658	0.017	0.008	0.043	0.14655	0.800

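### The stated 50 patients are described as 25 per intervention group plus 25 controls, which adds to 75; the total and the detectable effects are consistent, but the per-regimen size is wrong.

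*Protocol*

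**What the plan says.** The Protocol lists three groups: tPA50, tPA50 plus drip, and control ("Patients will be sequentially assigned to one the following three groups as follows"). Its sample-size paragraph then states "A sample size of 50 (25 in each intervention group and 25 in the control group) patients detects a >70% improvement". SAP 3.2 (Sample size) repeats the same split, "25 in each intervention group and 25 in the control group". In both documents the sentence goes on to attach the 70% figure to the two tPA groups together against controls, and to give a separate figure of more than 91% for the drip against controls.

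SAP 3.1 (Trial design) sets out the sequence. In stage one, "the first 10 patients will be randomly assigned to Group tPA50 or Control". The next 10 are again "assigned to Group tPA50 or Control when the second interim analysis is done". Patients 21 to 30 are randomized to the drip or control, after which "the trial progresses with patients being randomized to Group tPA50 plus drip or Control up to the final analysis at n=50". Under the November 2020 amendment, if the 48-hour primary outcome improves by at least 50% at 20 patients, the first-phase tPA50 regimen continues to 50 patients instead.

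Both documents plan for 50 eligible patients with a maximum of 60, and expect five centers to enroll 8 to 12 each.

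**The concern.** The word *each* assigns 25 patients to tPA50 and another 25 to the drip. With 25 controls that is 75 patients, which fits neither the total of 50 nor the maximum of 60. On neither path in the SAP do both regimens reach 25.

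The sentence is the plan's formal statement of its sample size. The trial is meant to help choose between regimens and to inform a Phase III trial. A reader who takes the parenthesis at face value will think the data on each regimen are larger than they will be. The gap matters most for tPA50 alone, because the plan gives no detectable effect that would correct the impression.

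**Working it through.** **Group sizes.** Stage sizes are from SAP 3.1. The allocation ratio is not stated; 1:1 is assumed, in line with 25 controls out of 50.

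| Patients | Comparison | tPA50 | Drip | Control |
|---|---|---|---|---|
| 1–10 | tPA50 v control | 5 | – | 5 |
| 11–20 | tPA50 v control | 5 | – | 5 |
| 21–30 | drip v control | – | 5 | 5 |
| 31–50 | drip v control | – | 10 | 10 |
| Total | | 10 | 15 | 25 |

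- As worded: 25 + 25 + 25 = 75.
- As planned: 10 + 15 + 25 = 50.
- If tPA50 is continued: 25 + 0 + 25 = 50.
- Center capacity: 5 × 8 to 5 × 12 = 40 to 60, also below 75.
- On the planned path the stated sizes are too high by (25 − 15)/25 = 40% for the drip and (25 − 10)/25 = 60% for tPA50.

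**Reproducing the printed effects.** Inputs from the sample-size sections: SD 100, baseline 149, design effect 1 + (5 − 1) × 0.03 = 1.12, about 20% loss to premature death, 80% power, two-sided, and the four boundaries in the SAP look table. Numerical integration with looks at 10, 20, 30 and 50 patients gives a standardized drift of 3.135 for 80% power (3.118 if looks are equally spaced).

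Detectable difference = 3.135 × 100 × √(1.12 × (1/m₁ + 1/m₂)), where m = 0.8 × the number randomized. Divide by 149 for the percentage.

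- 25 v 25 (m = 20 and 20): 313.5 × √0.1120 = 104.9 points = 70.4%. Printed: more than 70%. Equally spaced looks give 70.0%.
- 15 v 15 (m = 12 and 12): 313.5 × √0.1867 = 135.4 points = 90.9%. Printed: more than 91%.

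**Testing the 75-patient reading with the same formula.**

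- Pooled 50 v 25 (m = 40 and 20): 313.5 × √0.0840 = 90.9 points = 61.0%, not 70%.
- Drip 25 v 25: 70.4%, not 91%.
- Drip 15 against all 25 controls (m = 12 and 20): 313.5 × √0.1493 = 121.1 points = 81.3%, so the 91% uses concurrent controls only.

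The printed figures therefore fit 25 tPA patients in total and 15 on the drip. They do not fit 25 per regimen.

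**tPA50 alone, about 10 v 10 (m = 8 and 8).** The plan prints no figure. The answer depends on the test and looks assumed:

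| Assumption | Detectable, % of baseline |
|---|---|
| Four-look drift 3.135 | 111% |
| Two looks, boundaries 2.43798 and 2.42677, drift 3.21 | 114% |
| Single z-test at 0.05 | 99.5% |
| Single t-test at 0.05 | 108% |
| Single t-test at 0.015 | 133% |

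**The case against.** The strongest reply is that this is one wrong word in a parenthesis. The total of 50 is used consistently elsewhere, both printed effects reproduce from the true group sizes, and no boundary, analysis or enrollment target depends on the word. All of that stands.

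Three stronger readings are tempting, and the documents do not support them.

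- A reader might infer that the trial needs 75 patients or is undersized against its own calculation. It is not: the printed 70% and 91% come from 25 v 25 and 15 v 15.
- A reader might infer that the drip will be credited with 25 v 25 precision. The rest of the same sentence works against this. It ties 70% to both regimens together and gives the drip its own, weaker figure. The risk of misreading is mainly for tPA50 alone.
- A reader might quote 111% as the detectable effect for tPA50. That figure borrows a four-look drift for a comparison that, on the drip path, stops accruing at 20 patients after two looks. Only a range is defensible, and the plan never claimed power for this comparison.

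The counts 10 and 15 are also expectations. Besides the unstated ratio, randomization is within hospital in blocks of 10. If blocks are filled separately at each hospital (an assumption), incomplete blocks do not force an even split. With 20 patients spread as 4 at each of five hospitals, the variance of the tPA50 count is 5 × 4 × ¼ × 6/9 = 3.33 (SD 1.83), so about 6 to 14 patients could receive tPA50.

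What the reply does not remove is that a stated group size is wrong, in the sample-size statement of both documents, and contradicts the SAP's own sequence.

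**Conclusion.** The point holds as an error of description. Read literally, the sentence gives 75 patients where the plan has 50. It overstates the expected size of the drip group by 10 patients and of tPA50 by 15 on the planned path. If tPA50 is continued to 50 patients, that group does have 25 and the drip has none. The total and both printed detectable effects stand.

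The 75-versus-50 contradiction needs no assumption beyond there being two intervention groups. The 10/15 split rests on 1:1 allocation and on the drip being deployed. For tPA50 alone, the plan's inputs imply roughly 100% to 133% of baseline (111% to 114% with the printed boundaries). This is well above 70% under every choice tried, but it is not a figure the plan states. The correction should be made, and it changes nothing about how the trial is run.

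**What to change.** In the Protocol's Sample size and Power Analysis and in SAP 3.2 (Sample size), replace the parenthesis with text along these lines:

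> A total of 50: about 25 on tPA across both regimens (expected about 10 tPA50 and 15 tPA50 plus drip under SAP 3.1 with 1:1 allocation, or 25 and 0 if tPA50 is continued) and about 25 controls (about 10 and 15 concurrent).

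Then state that the figure above 70% is for all tPA pooled against all controls (25 v 25), and that the figure above 91% is for the drip against its concurrent controls (15 v 15). State the allocation ratio, since the expected counts depend on it.

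Optionally, add that tPA50 alone (about 10 v 10) has no stated detectable effect and that, with the plan's inputs, it would be roughly 100% to 133% of baseline depending on the test and looks assumed.

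The cost is a short rewording in each document, with no extra patients and no change to boundaries, analyses or conduct. The stated size per regimen becomes less favorable.
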